#### **6.3.1.1. Incidence of Adverse Events**

An overall summary of unsolicited TEAEs including the number and percentage of subjects who experience the following will be presented:

Confidential

- Any unsolicited TEAEs
- Any serious TEAEs
- Any fatal TEAEs
- Any TEAEs adjudicated as biopsy-proven organ rejection
- Any unsolicited medically-attended TEAEs
- Any Grade 3 or higher ARs or TEAEs
- Any unsolicited TEAEs leading to discontinuation from study vaccine
- Any unsolicited TEAEs leading to discontinuation from participation in the study
- Any unsolicited severe TEAEs

The table will also include number and percentage of subjects with unsolicited TEAEs that are treatment-related in each of the above categories. This table will also be presented by the subgroups named in [Section 6.1](#).

In addition, listings containing individual subject AE data for unsolicited AEs, unsolicited TEAEs leading to discontinuation from study vaccine, unsolicited TEAEs leading to discontinuation from participation in the study, serious AEs, unsolicited medically-attended AEs, and TEAEs adjudicated as biopsy-proven organ rejection will be provided, separately.

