7.5. Safety Definitions and Related Procedures

7.5.1. Adverse Event

An AE is defined as any untoward medical occurrence associated with the use of a drug in humans, whether or not it is considered drug-related.

Events Meeting the Adverse Event Definition

- Exacerbation of a chronic or intermittent pre-existing condition, including an increase in the frequency and/or severity of the condition.
- New conditions detected or diagnosed after the first dose of vaccine even though they may have been present before the start of the study.

Events NOT Meeting the Adverse Event Definition

- Medical or surgical procedure (eg, endoscopy, appendectomy): the condition that leads to the procedure should be the AE.
- Situations in which an untoward medical occurrence did not occur (social and/or convenience admission to a hospital).

An AR is any AE for which there is a reasonable possibility that the vaccine caused the AE ([Section 7.5.10](#)). For the purposes of investigational new drug safety reporting, “reasonable possibility” means that there is evidence to suggest a causal relationship between the vaccine and the AE.

An unsolicited AE is any AE reported by the participant that is not specified as a solicited AR in the protocol or is specified as a solicited AR but starts outside the protocol-defined period for reporting solicited ARs (ie, for the 7 days after each dose of vaccine).

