Source: Guidance for industry - Toxicity Grading Scale for Healthy Adult and Adolescent Volunteers Enrolled in Preventative Vaccine Clinical Trials ([DHHS 2007](#)).

Any solicited AR that meets any of the following criteria must be entered into the participant's source document and must also be recorded by the study site staff on the solicited AR page of the participant's eCRF:

- Solicited local or systemic AR that results in a visit to a healthcare practitioner (HCP; otherwise meets the definition of an MAAE)
- Solicited local or systemic AR leading to the participant withdrawing from the study or the participant being withdrawn from the study by the investigator (AE leading to withdrawal)
- Solicited local or systemic AR lasting beyond 7 days after injection
- Solicited local or systemic AR that leads to participant withdrawal from vaccine
- Solicited local or systemic AR that otherwise meets the definition of an SAE

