Any change in immunosuppressant medications	X
Any unsolicited treatment-related AE	X
Any treatment-related SAE	X
Discontinuation due to AE	X
Any severe AE	X
Any treatment-related severe AE	X

Abbreviations: AE = adverse event; AESI = adverse event of special interest; AR = adverse reaction; MAAE = medically attended adverse event; MedDRA = Medical Dictionary for Regulatory Activities; PT = preferred term; SAE = serious adverse event; SOC = system organ class.

Notes: X = results will be provided. Unsolicited AEs will be summarized by SOC and PT coded by MedDRA.

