#### 3.1. Primary Endpoints

The safety of 100 µg mRNA-1273 administered in 2-dose or 3-dose regimens will be evaluated by the following endpoints:

- Unsolicited AEs through 28 days after each injection
- Medically attended adverse events (MAAEs) from Day 1 and throughout the study period
- Serious adverse events (SAEs) from Day 1 and throughout the study period
- Adverse events of special interest (AESIs) from Day 1 and throughout the study period
- AEs leading to discontinuation from dosing and/or study participation (withdrawal) on Day 1 and throughout the study period
- Biopsy-proven organ rejection from Day 1 and throughout the study period

The reactogenicity of 100 µg mRNA-1273 administered in 2-dose or 3-dose regimens will be evaluated by the following endpoints:

- Solicited local and systemic ARs through 7 days after each injection (for unvaccinated participants who received 2 doses of mRNA-1273)
- Solicited local and systemic ARs through 7 days after each injection (for unvaccinated SOT recipients who received 3 doses and SOT recipients previously vaccinated outside the study who received a third booster dose)

The nAb responses to doses of 100 µg mRNA-1273 obtained 28 days after the second dose or third dose will be evaluated by the following endpoints:

- The geometric mean concentration (GMC) of serum SARS-CoV-2-specific nAb after the second dose (Day 57 for unvaccinated participants)
- The GMC of SARS-CoV-2-specific nAb 28 days after dose 3 (Day 113 for unvaccinated SOT recipients and Day 29 for previously vaccinated SOT recipients)

The safety of 100 µg BD of mRNA-1273 will be evaluated by the following endpoints:

- Unsolicited AEs through 28 days after BD injection
- MAAEs throughout the study period

- SAEs throughout the study period
- AESIs, including myocarditis/pericarditis throughout the study period
- AEs leading to discontinuation from dosing and/or study participation (withdrawal) throughout the study period
- Biopsy-proven organ rejection throughout the study period

The reactogenicity of 100 µg BD of mRNA-1273 will be evaluated by the following endpoint:

- Solicited local and systemic ARs through 7 days after BD injection

The nAb responses to 100 µg BD of mRNA-1273 obtained 28 days after the BD will be evaluated by the following endpoints:

- The GMC of serum SARS-CoV-2-specific nAb 28 days after the BD in SOT participants who received the Moderna primary series

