#### **6.3.1.2.TEAEs by System Organ Class and Preferred Term**

The following summary tables of TEAEs will be provided by SOC and PT using frequency counts and percentages (i.e., number and percentage of subjects with an event):

- All unsolicited TEAEs
- All unsolicited TEAEs by the subgroups named in [Section 6.1](#)
- All unsolicited TEAEs that are treatment-related
- All serious TEAEs
- All serious TEAEs that are treatment-related
- All unsolicited TEAEs leading to discontinuation from study vaccine
- All unsolicited TEAEs leading to discontinuation from participation in the study

Confidential

- All unsolicited Severe TEAEs
- All unsolicited Severe TEAEs that are treatment-related
- All unsolicited medically-attended TEAEs
- All unsolicited medically-attended TEAEs that are treatment-related
- All TEAEs adjudicated as biopsy-proven organ rejection
- All TEAEs that are AESI

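### The SAP's discontinuation tables count only unsolicited events, so the primary endpoint of AEs leading to discontinuation omits participants who stop because of a solicited reaction

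*SAP*

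**What the plan says.** SAP Section 3.1 lists among the Part A primary safety endpoints "AEs leading to discontinuation from dosing and/or study participation (withdrawal) on Day 1 and throughout the study period". The Part B wording is "AEs leading to discontinuation from dosing and/or study participation (withdrawal) throughout the study period". Protocol Table 1 has the same endpoint, and Protocol Table 6 (Section 8.3.2) plans its analysis under the row "Discontinuation due to AE".

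Protocol Section 7.5.1 separates the two kinds of event: "An unsolicited AE is any AE reported by the participant that is not specified as a solicited AR in the protocol", or a reaction of a solicited type that begins outside the 7-day reporting period. Protocol Section 7.5.3 lists solicited reactions that sites must enter on the solicited AR page of the eCRF. The list includes "Solicited local or systemic AR that leads to participant withdrawal from vaccine", and also a solicited reaction that ends study participation, which the protocol itself labels in parentheses as an AE leading to withdrawal.

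SAP Section 6.3.1.1 reports the endpoint as "Any unsolicited TEAEs leading to discontinuation from study vaccine", with a parallel row for leaving the study. The SOC/PT table in Section 6.3.1.2 is "All unsolicited TEAEs leading to discontinuation from study vaccine", again with a study-participation counterpart. The listings named in Section 6.3.1.1 have the same limit.

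**The concern.** The endpoint is defined over all AEs, but the outputs that report it cover only one of the two streams in which the trial records AEs. A participant who refuses the second dose because of fever or myalgia that began within a week of the first would be recorded by the site as the protocol requires, and would then be counted in none of the discontinuation tables.

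Reactogenicity is an obvious reason to stop a vaccine series, so the omitted events bear directly on what the endpoint is meant to show: how well the 2-dose, 3-dose and booster regimens are tolerated.

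**Working it through.** No planned figure has to be reproduced. The check sets the definitions beside the outputs.

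1. **Scope of the endpoint.** The wording in SAP Section 3.1 and Protocol Table 1 carries no limit to unsolicited events. Protocol Table 6 restricts some rows, for example "Any unsolicited treatment-related AE", but leaves "Discontinuation due to AE" unrestricted.

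2. **Does a solicited reaction qualify?** Yes. Protocol Section 7.5.1 defines an AR as a kind of AE, and Section 7.5.3 labels a solicited reaction that ends study participation as an AE leading to withdrawal.

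3. **Could it enter the tables as unsolicited?** Only if it starts after the 7-day period. A solicited reaction that starts within that period is excluded by the definition in Section 7.5.1.

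4. **Which SAP outputs would show it?**

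| SAP output | Would it show a stop caused by a solicited reaction? |
|---|---|
| 6.3.1.1 overall summary, vaccine and study discontinuation rows | No, unsolicited only |
| 6.3.1.1 discontinuation listings | No, unsolicited only |
| 6.3.1.2 SOC/PT discontinuation tables | No, unsolicited only |
| 6.3.1.1 row for Grade 3 or higher ARs or TEAEs | The reaction, if Grade 3 or higher; not the stop |
| 6.3.2 solicited AR tables and listing | The reaction (incidence, grade, onset, persistence, duration); not the stop |
| 6.2.1 disposition table and listing | The stop and a reason; not tied to the reaction record |

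 The Grade 3 row shows that ARs can be brought into this summary table, so its structure does not force the restriction.

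5. **Direction.** Each participant who stops solely because of a solicited reaction lowers the count by one, and nothing in the restriction can raise it. Protocol Section 7.5.3 and SAP Section 6.3.2 treat all solicited reactions as related to the injection, while the treatment-related counts in Section 6.3.1.1 are of unsolicited TEAEs. Those counts therefore lose some events that are related by definition.

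6. **Declaration.** SAP Section 7 declares no change from the protocol, and SAP Section 1 gives the SAP precedence where methods differ. The narrower count would take effect without notice.

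7. **Scale, by assumption only.** Let p be the share of participants who stop because of a solicited reaction; the documents give no value. With N = 220 transplant recipients, the expected number omitted is N × p, and the chance of omitting at least one is 1 − (1 − p)^N.

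| Assumed p | 220 × p | Chance of at least one omitted |
|---|---|---|
| 0.25% | 0.55 | 42% |
| 0.5% | 1.1 | 67% |
| 1% | 2.2 | 89% |
| 2% | 4.4 | 99% |

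 For stopping *dosing*, 220 is too large if it includes Group B4, whose members receive a single study dose. If the planned minimum of 50 recipients with a non-Moderna series sits within the 220, which the text leaves unclear, at most 220 − 50 = 170 could stop dosing. That gives 170 × 0.5% = 0.85 to 170 × 2% = 3.4.

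**The case against.** The strongest reply is that these participants are not lost. SAP Section 6.2.1 tabulates, by participant group, those who stop before the second or third dose and those who leave the study, with reasons, and lists them individually. Protocol Sections 6.2 and 6.3 require the reason to be recorded, and for study withdrawal the AE option asks for the event. SAP Section 6.3.2 also lists the solicited reactions. This stands as a limit: a reader might infer that such participants vanish from reporting, and they do not. It does not remove the point. Disposition is not the endpoint analysis, its dosing row stops at the third dose, and it does not separate solicited from unsolicited causes. It could show AE withdrawals that the AE tables lack.

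Unqualified endpoint wording is also not decisive alone. The MAAE endpoint is unqualified too, yet Protocol Table 6 analyses unsolicited MAAEs. That is fair; the case rests more on Section 7.5.3 and on the missing qualifier in the discontinuation row.

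Three further inferences should be resisted:

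- *The treatment-related row loses all its related events.* It does not. Related unsolicited events stay in, including solicited-type reactions that begin after the 7-day period.
- *Anyone who declines dose 3 after a reaction is a missed discontinuation.* For unvaccinated recipients dose 3 was first an offer, and those who decline it form Group A1. The example is secure for dose 2, and for dose 3 only where three doses were planned or consented to.
- *Booster reactions lead to stopping dosing.* No study dose follows the booster, so only study withdrawal can be affected.

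Finally, safety is descriptive, with no hypothesis test. No decision rule changes, which limits the consequence.

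**Conclusion.** The point holds as a mismatch between a primary safety endpoint and the tables that report it. As written, the SAP can only undercount AEs leading to discontinuation, and the omitted events include some that are related by definition.

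The size is unknown. The range in the working is illustrative and rests on assumed rates. A reader might take the Grade 3 frequencies quoted from Study P301 as support for it, but those are incidences of severe reactions and say nothing about how many people stop. Dosing discontinuation can be affected only in participants with a further planned dose; study withdrawal can be affected in anyone. With counts likely to be small, one omitted case could still turn a reported zero into a wrong zero. The SAP should be corrected, but the conclusions of the trial do not hang on it.

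**What to change.** In SAP Section 6.3.1.1, add rows for any AE, whether solicited AR or unsolicited TEAE, leading to discontinuation from study vaccine and, separately, from study participation. Give each row solicited and unsolicited sub-rows, and take the solicited events from the solicited AR page of the eCRF. Carry them into the treatment-related counts, and extend the Section 6.3.1.2 tables and the listings to match.

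If the sponsor intends unsolicited events only, restate the endpoint that way and declare the change in SAP Section 7. Protocol Section 8 also calls for a protocol amendment when methods tied to the primary objectives change.

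The cost is one extra source dataset in existing tables, using data already collected. The reported discontinuation rate may become slightly less favourable.

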#### **6.3.1.2.TEAEs by System Organ Class and Preferred Term**

The following summary tables of TEAEs will be provided by SOC and PT using frequency counts and percentages (i.e., number and percentage of subjects with an event):

- All unsolicited TEAEs
- All unsolicited TEAEs by the subgroups named in [Section 6.1](#)
- All unsolicited TEAEs that are treatment-related
- All serious TEAEs
- All serious TEAEs that are treatment-related
- All unsolicited TEAEs leading to discontinuation from study vaccine
- All unsolicited TEAEs leading to discontinuation from participation in the study

Confidential

- All unsolicited Severe TEAEs
- All unsolicited Severe TEAEs that are treatment-related
- All unsolicited medically-attended TEAEs
- All unsolicited medically-attended TEAEs that are treatment-related
- All TEAEs adjudicated as biopsy-proven organ rejection
- All TEAEs that are AESI

#### **6.3.1.3. TEAEs by Preferred Term**

A summary table of all unsolicited TEAEs by PT only will be provided. PTs will be sorted in a descending order according to the overall frequency.

#### **6.3.1.4. TEAEs by System Organ Class, Preferred Term and Severity (or Grade)**

The following summary tables of TEAEs will be provided by SOC, PT, and maximum severity (mild < moderate < severe) or grade using frequency counts and percentages:

- All unsolicited TEAEs
- All unsolicited TEAEs that are treatment-related

#### **6.3.2. Solicited Adverse Reactions**

Solicited ARs are collected for the purpose of assessing reactogenicity. All listings and summaries of solicited ARs will be based on the Solicited Safety Set.

An AR is any AE for which there is a reasonable possibility that the test product caused the AE. The term “Solicited Adverse Reactions” refers to selected signs and symptoms occurring after injection administration during a specified post-injection follow-up period (day of injection and 6 subsequent days). The solicited ARs are recorded by the subject in eDiary. The occurrence and intensity of selected signs and symptoms is actively solicited from the participant during a specified post-injection follow-up period (day of injection and 6 subsequent days), using a pre-defined checklist (i.e., solicited ARs).

The following local ARs will be solicited by the eDiary: pain at injection site, erythema (redness) at injection site, swelling (hardness) at injection site, and localized axillary swelling or tenderness ipsilateral to the injection arm.

Confidential

The following systemic ARs will be solicited by the eDiary: headache, fatigue, myalgia (muscle aches all over the body), arthralgia (aching in several joints), nausea/vomiting, fever, and chills.

The solicited ARs will be graded based on the grading scales presented in Table 3 in Protocol Amendment 4, modified from the Toxicity Grading Scale for Healthy Adult and Adolescent Volunteers Enrolled in Preventative Vaccine Clinical Trials (DHHS 2007). The investigator will assess Grade 4 events (with exception of fever).

If a solicited local or systemic AR continues beyond 7 days post-injection, the participant will be prompted to capture solicited local or systemic AR in the eDiary until resolution.

All solicited ARs (local and systemic) will be considered causally related to study injection.

Analyses of solicited ARs will be provided by participant group for each injection (first, second, third, or BD) based on the associated subset of Solicited Safety Set, i.e. First, Second, Third Study Injection Solicited Safety Set, or Booster Injection Solicited Safety Set; and for any injection based on the Any Study Injection Solicited Safety Set, unless otherwise specified.

The number and percentage of subjects who reported each individual solicited local AR (has a severity grade of Grade 1 or greater) and solicited systemic AR (has a severity grade of Grade 1 or greater) during the 7-day follow-up period after each injection will be tabulated by participant group and severity grade.

The number and percentage of subjects who reported each individual solicited AR will also be summarized by participant group, severity grade, and day of reporting.

A two-sided 95% exact confidence interval (CI) using the Clopper-Pearson method will be provided for the percentage of subjects who reported any solicited local AR, solicited systemic AR, or any solicited AR.

The onset of individual solicited AR is defined as the time point after each injection at which the respective solicited AR first occurred. The number and percentage of subjects with onset of individual solicited AR will be summarized by participant group and study day relative to the corresponding injection (Day 1 through Day 7).

The number and percentage of participants experiencing solicited ARs persisting beyond 7 days after each injection will be summarized.

Confidential

The number of days reporting each solicited AR will be summarized descriptively. The number of days will be calculated as the days of the solicited AR is reported within the 7 days of injection including the day of injection, no matter if it is intermittent or continued. If the solicited AR continues beyond 7 days, the days a solicited AR is reported after 7 days will be included (e.g., in the case of an event that lasted 5 days in the first 7 days post-injection and 3 days beyond 7 days post-injection, the duration will be reported as 8 (5 + 3) days). In addition, the duration for each solicited AR that started within 7 days of injection will be summarized descriptively. The duration of the solicited AR will be calculated as the last day – the first day + 1.

Solicited ARs occurring within 7 days following the first, second, third study injection will be presented by the subgroups described in [Section 6.1](#). Likewise, solicited ARs occurring within 7 days following the BD will also be presented in this manner.

Solicited ARs will be listed for the Safety Set/ Solicited Safety Set.

### **6.3.3. Clinical Laboratory Results**

Clinical laboratory samples will be collected at the Day 1 visit and at post-baseline visits through the Day 57 visit for participants receiving 2 doses of IP, or through Day 113 visit for participants receiving 3 doses of IP, or through Day 29 visit for SOT participants that are previously vaccinated with Moderna COVID-19 vaccines. For participants that continue to Part B of the study and receive BD, clinical laboratory samples will be collected at BD-Day 1, BD-Day 8, and BD-Day 29. Results will be summarized using descriptive statistics at each visit by participant group and will be presented in a data listing for the Safety Set.

Using the Toxicity Grading Scale for Healthy Adult and Adolescent Volunteers Enrolled in Preventative Vaccine Clinical Trials (DHHS 2007), as described in [Table 5](#), the number and percentage of participants experiencing clinical laboratory abnormalities and changes from baseline values at each visit will be summarized by severity grade and participant group. Similarly, clinical laboratory toxicity will be summarized as the maximum over all post-injection visits. Clinical laboratory results and their toxicity grades will also be listed for the Safety Set.

